8.4 Demographics and Baseline Characteristics

Demographic data include illness severity score (APACHE II), age, gender, race, height, weight and body mass index (BMI) calculated as weight (kg)/height² (m), and ethnicity.

Other baseline/screening data include:

- 1. Underlying disease.
- 2. Known allergies.

- 3. Current medications and medications prescribed during the 7-day window prior to informed consent and those relevant to ICU admission.
- 4. General medical history; medical conditions or surgical procedures.
- 5. Vital signs including height, weight, blood pressure, pulse rate, temperature, and respiratory rate.
- 6. Physical exam.
- 7. Laboratory parameters, see Appendix 1.

Continuous variables will typically be summarized by treatment group using the number of subjects n, mean, standard deviation, minimum, median and maximum and a t-test or Wilcoxon rank sum test will be used to evaluate mean differences between groups, as applicable. Frequency and percentages will be provided for the categorical variables by treatment group and a Fisher's exact test will be used to evaluate differences between treatment groups.

Demographics and Baseline Characteristics will be summarized by randomized treatment group, and for the FA Set only.

8.5 Efficacy Endpoints

8.5.1 Primary Efficacy Endpoint

The primary endpoint of the study, extracorporeal circuit life, will be analyzed as a time-to-event endpoint (survival analysis).

In the statistical analysis extracorporeal circuit life of a filter that is replaced due to continuous use for 72 hours, will be censored. Likewise, filters that are in use when the end of the observation period of 120 hours is reached, will be censored at their current duration of usage at the end of the observation period. Filters that are replaced any time CRRT is stopped for reasons other than filter clotting (including drop-outs), will be censored at their current duration of usage. Only filters that are replaced due to filter clotting or excessive transmembrane pressure as indicated by one or both Prismaflex System alarms/conditions as defined under Section 6.7.1 Primary Efficacy Endpoint and for whom alarm causes have been confirmed by an Independent Adjudicator, will be considered 'events' in terms of the statistical analysis.

Each filter used during the 120 hours observation period or until treatment is finished will be included in the statistical analysis (several filters per patient).

Separate estimates per treatment group will be provided for the primary endpoint based on Kaplan-Meier methodology. Differences between treatment groups will be assessed using a clustered log-rank test in order to account for the potential dependence among extracorporeal circuit lives of the same patient.[19]

Analyses of the primary endpoint will be carried out on the FA Set based on the randomized treatment groups (intent-to-treat principle).

An interim analysis will be carried out after 50% of subjects completed treatment. Please refer to Section 8.8 for further details regarding the interim analysis.

The study will be stopped early due to overwhelming efficacy when a p value of < 0.0087 is observed using the clustered log-rank test at the interim analysis, see section 8.8 (critical value based on Bauer & Kohne procedure with no early stopping for futility). If $p \ge 0.0087$ and the study continues enrollment into a second stage, Fisher's combination test will be performed at the end of the study using a critical value of 0.0087 which guarantees that the overall type 1 error is controlled and preserved at a maximum of 0.05.[18]

The analysis of the primary endpoint will be repeated using the PP Set as a sensitivity analysis. In order to assess a potential impact of informative censoring on the primary efficacy analysis, a sensitivity analysis will be carried out on the FA Set using different assumptions for cases where therapy (ie, a filter) was discontinued for reasons other than circuit clotting. Further details will be provided in the SAP.

8.5.2 Secondary Efficacy Endpoints

A descriptive summary of systemic and post-filter blood iCa concentrations as assessed baseline (systemic only), initiation (systemic only), 1 hour and every 6 hours from the initiation of study CRRT during the 120 hour Treatment Period and at 120 hours or end of the Treatment Period will be provided by treatment group. Post-filter blood iCa concentrations will only be presented for the Prismocitrate 18 Arm.

A mixed-effects model repeated measures (MMRM) analysis will be used to evaluate differences between treatment groups in the change from initiation of study CRRT in systemic iCa concentrations that are collected 1 hour and every 6 hours from the initiation of study CRRT during the 120 hours Treatment Period and at 120 hours or end of the Treatment Period. If justified, separate models will be carried out for patients who did and did not receive standard-of-care CRRT.

In addition, frequencies and percentages will be provided for systemic iCa < 1.1 mmol/L by time point and treatment group (threshold indicative of decrease in iCa despite adequate calcium compensation).

A descriptive summary of the daily delivered dose and overall delivered dose will be provided by treatment group. Differences between treatment groups in the percentage of overall prescribed dose actually administered will be assessed on a 5% significance level using a two-sided t-test or Wilcoxon rank sum test, as applicable. However, the statistical test will only be carried out conditional upon a significant test result for the primary endpoint at the time point of the interim analysis or final analysis. This hierarchical test procedure guarantees that the overall type 1 error is controlled and preserved at a maximum of 5%.

Secondary Efficacy Endpoints will be analyzed on the FA Set based on the randomized treatment groups (intent-to-treat principle).

8.6 Safety Endpoints

Analysis of safety endpoints will be carried out on the FA Set based on the actual treatment groups for the following parameters:

- 1. A MMRM analysis will be used to evaluate differences between treatment groups in the change from baseline in serum bicarbonate and pH that are collected every 6 hours from the initiation of study CRRT during the 120 hour Treatment Period and at 120 hours or end of the Treatment Period. Frequencies and percentages will be provided for pH < 7.2 by time point and treatment group (thresholds indicative of metabolic acidosis).
- 2. A MMRM analysis will be used to evaluate differences between treatment groups in the change from baseline in blood total calcium concentrations that are assessed at 1 hour and every 6 hours from the initiation of study CRRT during the 120 hour Treatment Period and at 120 hours or end of the Treatment Period.
- 3. A MMRM analysis will be used to evaluate differences between treatment groups in the change from baseline in serum electrolytes (sodium, potassium, chloride, phosphate, and magnesium) that are collected every 6 hours from the initiation of study CRRT during the 120 hour Treatment Period and at 120 hours or end of the Treatment Period.

- 4. A descriptive summary of the total calcium/systemic iCa ratio as assessed at baseline, at initiation of study CRRT, 1 hour and every 6 hours from the initiation of study CRRT during the 120 hour Treatment Period and at 120 hours or end of the Treatment Period will be provided by treatment group. Frequencies and percentages will be provided for total calcium/systemic iCa ratio > 2.1 by time point and treatment group (threshold suggestive of citrate accumulation). Frequencies and percentages will be provided for anion gap > 11 mmol/L by time point and treatment group (threshold indicative of metabolic disturbance) as well as for base excess < -5 mmol/L.
- 5. A descriptive summary of the number, location, and duration of bleeding events along with the estimated blood loss during the 120 hour Treatment period will be provided by treatment group. The number and type of blood transfusion along with the number of units infused will also be summarized.
- 6. An analysis of covariance (ANCOVA) model will be used to evaluate differences between treatment groups in the change from baseline to final measurement in laboratory and vital signs measurements.
- 7. Adverse events will be mapped to a primary SOC and Preferred Term according to MedDRA and will be summarized.

8.7 Analysis of Training on Administration of Prismocitrate 18

A descriptive summary of proficient completion of training on the administration of Prismocitrate 18 will be provided.

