5.2.3 Monitoring of Therapy

Systemic iCa levels will be measured at baseline, initiation, and systemic and post-filter blood iCa levels will be measure 1 hour after initiation of study CRRT (post-randomization) and then every 6 hours thereafter and at 120 hours or end of Treatment Period. The pH and bicarbonate should be measured at baseline, initiation, and every 6 hours during the 120 hour Treatment Period and at 120 hours or end of Treatment Period. Health care professionals managing the patient should be instructed to notify the clinician immediately if the serum pH is < 7.20 or > 7.45, serum bicarbonate is < 15 or > 35 mmol/L, and/or the systemic blood iCa is < 0.9 or > 1.3 mmol/L.

Citrate metabolism may be impaired in patients with moderate to severe liver failure. The additional steps outlined below are needed to monitor specifically for the potential development of citrate accumulation, not only in these patients but in the entire study

population. Blood total calcium concentrations will be measured at baseline, initiation, 1 hour and every 6 hours during the 120 hour Treatment Period and at 120 hours or end of the Treatment Period from the initiation of study CRRT. In conjunction with simultaneous systemic iCa concentrations, the total calcium/iCa ratio (both measurements in mmol/L) will be determined as an indicator of citrate accumulation and health care professionals managing the patient should be instructed to notify the clinician for any value above 2. 1. Moreover, based on the clinical judgement of the managing physician, this threshold value should also prompt an immediate CRRT prescription change designed to correct the metabolic disturbance. One of the following prescription changes should occur:

- Decrease in the Prismocitrate infusion rate; or
- Increase in the BFR; or
- Increase in the dialysate flow rate

The effect of one of these changes should be assessed with ongoing monitoring of relevant clinical and laboratory parameters - if improvement does not occur within two (2) hours, the Prismocitrate infusion should be stopped.

When a total calcium/iCa ratio of more than 2.1 is reported, any one of the following abnormalities reported concurrently should heighten the clinical suspicion of citrate accumulation and reinforce the need to undertake the steps outlined above:

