Appendix 1 Blood Sampling Schedule

 	1	t	 	
Parameter	Before Randomization	After Randomization But Before Initiation of Study CRRT ^a	During Study CRRT ^b	End of Study CRRT During Treatment Period
Complete Blood Count (CBC) and blood lactate measurement	Screening			
pH and base excess (ABG or VBG)		Baseline and Initiation	At 6, 12, 18, 24, 30, 36, 42, 48, 54, 60, 66, 72, 78, 84, 90, 96, 102, 108, 114, & 120 hours ^b	When Study CRRT is terminated
Serum bicarbonate		Baseline and Initiation	At 6, 12, 18, 24, 30, 36, 42, 48, 54, 60, 66, 72, 78, 84, 90, 96, 102, 108, 114, & 120 hours ^b	When Study CRRT is terminated
Systemic iCa ²⁺		Baseline, 1 hour prior to initiation of Study CRRT	At 1, 6, 12, 18, 24, 30, 36, 42, 48, 54, 60, 66, 72, 78, 84, 90, 96, 102, 108, 114, & 120 hours ^b	When Study CRRT is terminated
Post-Filter iCa ²⁺ Prismocitrate 18 Arm Only			At 1, 6, 12, 18, 24, 30, 36, 42, 48, 54, 60, 66, 72, 78, 84, 90, 96, 102, 108, 114, & 120 hours ^b	When Study CRRT is terminated
Serum Electrolytes: Sodium, Potassium, Chloride, Phosphate, Magnesium, & Anion Gap		Baseline and Initiation	At 6, 12, 18, 24, 30, 36, 42, 48, 54, 60, 66 72, 78, 84, 90, 96, 102, 108, 114, & 120 hours ^b	When Study CRRT is terminated

Parameter	Before Randomization	After Randomization But Before Initiation of Study CRRT ^a	During Study CRRT ^b	End of Study CRRT During Treatment Period
Creatinine & BUN		Baseline and Initiation	Twice daily	When Study CRRT is terminated
Bleeding Parameters: PT/INR, PTT, hemoglobin, hematocrit, platelet count	Screening	Baseline and Initiation	At least once daily	When Study CRRT is terminated
Blood total calcium Total calcium/iCa ²⁺ ratio	Screening	Baseline and Initiation	At 1, 6, 12, 18, 24, 30, 36, 42, 48, 54, 60, 66 72, 78, 84, 90, 96, 102, 108, 114, & 120 hours ^b	When Study CRRT is terminated

Parameter	Before Randomization	After Randomization But Before Initiation of Study CRRT ^a	During Study CRRT ^b	End of Study CRRT During Treatment Period
Liver function tests (Alanine transaminase [ALT], Aspartate transaminase [AST], Alkaline phosphatase [ALP] and total bilirubin	Screening	Baseline	As determined by local standard-of- care	As determined by local standard-of- care

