14.3 Serum Bicarbonate, pH, Blood Total Calcium and Serum Electrolytes

Serum bicarbonate, pH (ABG), blood total calcium concentrations and serum electrolytes (sodium, potassium, chloride, phosphate, magnesium) will be analyzed in the exact same manner as blood iCa²⁺ concentrations.

Along the lines of Section 13.3 Secondary Analysis descriptive summaries will be carried out for each parameter at the different assessment time points, and changes from baseline will be analyzed. A MMRM analysis will be deployed for the different parameters following the description under Section 13.3.

The total calcium/iCa²⁺ ratio will only be summarized descriptively. Frequencies and percentages will be provided for pH < 7.2 by time point and treatment group (threshold indicative of metabolic acidosis). Frequencies and percentages will further be provided for total calcium/iCa ratio > 2.1 by time point and treatment group (threshold suggestive of citrate accumulation) as well as for anion gap > 11 mmol/L (threshold indicative of metabolic disturbance) and base excess < -5 mmol/L.

Complete blood count and blood lactate measurements obtained at screening will be listed by patient.

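### Citrate-accumulation flags are tabulated by time point only, so the share of patients who ever crossed a threshold cannot be read from the planned output

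*Protocol*

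**What the plan says.** Protocol 2.2 sets out to evaluate whether citrate accumulation develops, using the total calcium/ionized calcium ratio, anion gap and base excess together with pH. The planned summaries are these:

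- **Protocol 8.6 item 4:** "Frequencies and percentages will be provided for total calcium/systemic iCa ratio > 2.1 by time point and treatment group". Anion gap is handled by time point as well. Base excess is added at the end of the sentence and is not explicitly tied to time points.
- **SAP 14.3:** "Frequencies and percentages will further be provided for total calcium/iCa ratio > 2.1 by time point and treatment group", continuing "as well as for anion gap > 11 mmol/L (threshold indicative of metabolic disturbance) and base excess < -5 mmol/L". It also says that the ratio "ratio will only be summarized descriptively" is the plan for that variable, so it has no repeated-measures model.
- **SAP 8.5:** values from additional draws stay out of descriptive summaries. They are listed and enter the repeated-measures models.
- **SAP 8.2:** missing values are not imputed.
- **Protocol Appendix 1 and SAP Table 2:** the ratio is sampled on a fixed schedule and again "When Study CRRT is terminated". SAP Table 2 footnote c substitutes the last available treatment-period value if that sample was not taken.
- **Protocol 5.2.3:** for a ratio above 2.1, and subject to the physician's judgement, "this threshold value should also prompt an immediate CRRT prescription change designed to correct the metabolic disturbance". The Prismocitrate infusion is to stop if there is no improvement within two hours.

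No text, table title or listing title defines a patient-level count over the whole treatment period, a worst value, or a time to first flag.

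**The concern.** Whether accumulation develops is a question about patients, and the planned tables answer a different one: how many patients are past the threshold at a given sampling time. The two differ most for an abnormality that is meant to be corrected quickly. Under protocol 5.2.3 a flag leads to a prescription change aimed at reversing it. With sampling every six hours, a successful correction may leave the flag visible in a single row.

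The rows cannot simply be added, because a persistent case appears in several and a short one in only one. A ratio above 2.1 found only on an extra draw enters no flag table and, since the ratio has no model, no analysis either; it is only listed. At stake is the proportion of patients in each arm who developed the product's specific metabolic harm, and the difference between arms.

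**Working it through.** The documents state no figure for this point, so there is nothing to reproduce. Two checks size the gap.

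**1. A bound on scheduled samples that needs no flag rate**

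Inputs: 80 patients per arm (protocol 8.2). The schedule reads "At 1, 6, 12, 18, 24, 30, 36, 42, 48, 54, 60, 66" and continues every six hours to 120 h (Appendix 1), which gives 1 + 120/6 = 21 scheduled samples.

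Let x_t be the number flagged in row t, and E the number ever flagged on a scheduled sample. Then max(x_t) ≤ E ≤ min(80, Σx_t).

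Take one flagged patient in every row, with all 80 still sampled, so that each row shows 1/80 = 1.25%:

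- Lower limit: the same patient each time, E = 1, or 1/80 = 1.25%.
- Upper limit: a different patient each time, E = 21, or 21/80 = 26.25%.

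With two patients per row (2.5%) the limits are 2/80 = 2.5% and 42/80 = 52.5%. If all 80 reach 120 h and the end-of-treatment value is the 120 h value, the end-of-treatment row is also 1.25% in both extremes of the first case, so it does not separate them.

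**2. What the end-of-treatment row recovers**

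This was simulated over the 21 samples with 200,000 patients per setting. Every rate is an assumption: onset probability 0.5%, 1% or 2% per sample; one episode per patient lasting one or two samples; 30% or 60% off study CRRT by 120 h for other reasons; and 0%, 50% or 100% of flagged patients leaving study CRRT before the next sample. The end-of-treatment value is taken as the last scheduled value, as footnote c would do. One middle setting (onset 1%, one-sample episode, 30% background stopping) gives:

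| Flagged patients who stop study CRRT | Ever flagged | Highest scheduled row | End-of-treatment row |
|---|---|---|---|
| All | 16.0% | 1.0% | 16.0% |
| Half | 16.2% | 1.0% | 8.5% |
| None | 16.1% | 1.0% | 0.8% |

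Over all settings, about 7% to 29% are ever flagged and the highest scheduled row is about 0.5% to 4%. The end-of-treatment row is about 7% to 30% if all flagged patients stop (essentially equal to ever flagged), about 4% to 16% if half do, and about 0.5% to 3% if none do.

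The end-of-treatment row is therefore a good substitute only when a flag ends study CRRT. It fails when the correction works and treatment continues.

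**The case against.** **Patients who stop are not lost.** A reader might infer that anyone taken off study CRRT drops out of the tables. The documents do not support this. A termination sample is scheduled, the end of the Treatment Period is a named time point in item 4, and footnote c fills a gap with the last value. These patients leave only the later scheduled rows. Even that is an inference from the no-imputation rule, because neither document states the row denominator.

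**No fixed understatement follows.** It is tempting to compare the ever-affected share with the average scheduled row. Assume that 15% would accumulate and that each case leaves study CRRT after one flagged sample: about 10.3% are affected and the average row is 0.8%. But the end-of-treatment row is then also 10.3%. It falls to 5.4% if half of flagged patients stop and 0.4% if none do. No planned output averages the rows.

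**Protocol 5.2.3 does not make a flag end study CRRT.** The stop is conditional and applies to the Prismocitrate infusion. SAP 13.1 provides for filters used after a switch of treatment, so sampling may continue.

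**Other outputs help in part.** Laboratory abnormalities that need intervention qualify as adverse events (protocol 6.10), and SAP 14.1 counts subjects with at least one event. That route depends on investigator reporting in an open-label trial, and citrate accumulation is not on the anticipated-event list in 6.10.6. Listing 16.2.8.3 would allow a later derivation, but not a prespecified one. The repeated-measures models for pH, total calcium and related variables estimate mean changes, not the proportion past a threshold.

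**Presenting illness.** Protocol 1.1 notes that metabolic acidosis is common with AKI. A reader might conclude that the pH, anion gap and base excess rows mostly reflect the state at entry. The documents give no rate at Initiation, so this cannot be claimed. It is only a reason to show new crossings separately.

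**Conclusion.** The point holds as a gap in reporting. The plan gives flags by time point and no per-patient count, so the share of patients who developed a flag is not identified: 1.25% in every row is compatible with 1.25% to 26.25% ever affected. That range rests only on 80 patients sampled at 21 scheduled times. The simulated ranges rest on assumed onset, duration and stopping rates and show direction, not an expected result.

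Two kinds of case are missed: flags corrected before treatment ends are not counted per patient in any row, and flags seen only on additional draws reach no flag table. Cases in which a flag ends study CRRT should be visible in the end-of-treatment row. The planned tables are not wrong; they do not by themselves answer the protocol 2.2 question.

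**What to change.** In protocol 8.6 item 4 and SAP 14.3 (Tables 14.2.12.2 to 14.2.12.5), for each threshold:

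1. Add the number and percentage of treated patients with at least one value past the threshold after Initiation, from scheduled or additional draws, by actual treatment group, with the risk difference and 95% confidence interval.
2. Report the same among patients not past the threshold at Initiation.
3. Show the count from scheduled samples alone beside it.
4. Print the number of patients sampled in each by-time-point row, and say explicitly that base excess is tabulated by time point too.

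Time to first ratio above 2.1 would be a useful but optional addition.

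The cost is SAP wording and one added block per existing table; no new data are needed and no clinical rule changes. The drawback is that the arms may differ in the number of unscheduled draws, which gives one arm more chances to show a flag. Item 3 lets the reader see how much of a difference between arms could come from that.

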8.8 Interim Analysis

A single interim analysis will be conducted when 50% of patients have completed treatment. The purpose of the interim analysis is to evaluate the primary efficacy endpoint for overwhelming efficacy, or the need to adjust the sample size. If the primary analysis yields a statistically significant test result (p < 0.0087, critical value for clustered log rank test based on Bauer & Kohne procedure with no early stopping for futility) on the FA Set, and if further no safety concern or other considerations require continuation of enrollment, the study will be stopped for overwhelming efficacy. Otherwise enrollment of subjects will continue and the whole statistical analysis as described in this document will be carried out at the end of the study using Fisher's combination test.[18] This approach guarantees that an overall type 1 error of 0.05 is preserved.

Sample size re-estimation at the interim analysis will be based on Fisher's criterion (Fisher's combination test). Simulation studies will be run utilizing the p value observed at the interim analysis (p1) and the initial assumptions for median survival times in the two treatment groups (in the Prismocitrate 18 and Control group). Re-assessment of the sample size will target a conditional power of 90% for rejecting the null hypothesis given the observed p value of the interim analysis.

